8.5.3.2 Vital Signs

Measurements for vital signs as well as changes from baseline will be summarized with descriptive statistics: mean, standard deviation, minimum, median, and maximum values by time point and treatment arm, for the Safety population. Baseline is defined as the last measurement prior to the first treatment administration. These summaries will be performed according to Phase. For the Phase 3 segment, the analyses listed above will also be performed according to SARS-CoV-2 serostatus at baseline.

8.5.4 **DISPOSITION**

Disposition will be summarized by treatment arm for the ITT population and will include the number and percentage randomized, the number and percentage who received each dose and the number who completed the trial. The number and percentage of subjects who discontinued will be summarized overall and by reason. The number in each analysis population will also be presented. These summaries will be performed according to Phase. For the Phase 3 segment, the analyses listed above will also be performed according to SARS-CoV-2 serostatus at baseline.

8.5.5 **DEMOGRAPHIC AND OTHER BASELINE CHARACTERISTICS**

8.5.5.1 Demographics

Demographic data will be summarized with descriptive statistics: mean standard deviation, minimum, median, and maximum values for continuous variables, and percentages for categorical variables, by treatment arm, for the ITT and PP populations. These summaries will be performed according to Phase. For the Phase 3 segment, the analyses listed above will also be performed according to SARS-CoV-2 serostatus at baseline.

8.5.5.2 Prior Medications

Prior medications are those that were used before the start of the trial (prior to Day 0). Partial stop dates of prior medications will be assumed to be the latest possible date consistent with the partial date; start dates will not be imputed. Data for all prior medications will be summarized with percentages by treatment arm, for the ITT and PP populations. These summaries will be performed according to Phase. For the Phase 3 segment, the analyses listed above will also be performed according to SARS-CoV-2 serostatus at baseline.

8.5.6 INTERIM ANALYSES

For safety issues, the DSMB could recommend stopping enrollment at any time; no formal interim analysis will be performed for this purpose. The two-sided type I error of 0.05 will not be adjusted for possible early stopping due to this aspect.

For the Phase 2 segment, group-level unblinded summaries of the immunogenicity and safety data will be produced once Week 6 visit immunology data and Week 8 visit safety data are complete for all subjects who have not discontinued, while maintaining subject-level blinding. Long-term follow-up data will continue to be collected for all subjects who have not discontinued with remaining visits through the final visit. These summaries will allow the Sponsor to have results for the purposes of dose selection for the Phase 3

INO-4800	COVID19-311
Inovio Pharmaceuticals, Inc.	Clinical Protocol

portion. No subject-level immunogenicity data will be produced, and subject-level immunogenicity data will not be available in the clinical trial database until all other clinical trial data are finalized at the end of the trial. No safety summary will be provided if the total number of subjects who experience the event of interest is greater than 0 and the count of the number of subjects with the event in a given treatment group relative to the total produces a percentage less than 3%, for a given summary. The group-level unblinded production of the summaries will not include anyone directly involved with the trial or any additional unblinded personnel; only the external Contract Research Organization (CRO), ICON, which will already be providing unblinded summaries for the Data Safety Monitoring Board, will be utilized. Thus, the trial will remain blinded to the Sponsor with respect to subject treatment assignment.

For the Phase 3 segment, there are two planned formal interim efficacy analyses: one at 50% (75 cases) and one at 75% (112 cases) of the total required for the primary endpoint (149 cases). The Lan-DeMets O'Brien-Fleming approximate alpha-spending function will be used for the efficacy and futility boundaries. As such, the first interim analysis will utilize a one-sided nominal alpha of 0.0016, and the second interim analysis will utilize a one-sided nominal alpha of 0.0092. The final analysis will utilize a one-sided nominal alpha of 0.0092. The final analysis will utilize a one-sided nominal alpha of 0.0092. The final analysis will utilize a one-sided nominal alpha of 0.022. The DSMB will be responsible for the interim evaluations. The unblinded interim analyses will not include anyone directly involved with the trial or any additional unblinded personnel; only the external Contract Research Organization (CRO), ICON, which will already be providing unblinded summaries for the Data Safety Monitoring Board, will be utilized. Thus, the trial will remain blinded to the Sponsor with respect to subject treatment assignment.

If the prespecified criteria for efficacy above are met at either interim analysis, then enrollment will continue until 4500 subjects have been enrolled, and blinded follow-up will continue until 4500 subjects have 6 months of safety follow-up. At that point, the trial would be unblinded, and subjects who received placebo will be offered the active product.

8.5.7 MULTIPLICITY

There is one primary hypothesis that will be tested. As there are two interim analyses of the primary endpoint, the type I error rate will be controlled at two-sided 0.05 by using the Lan-DeMets O'Brien-Fleming approximate alpha-spending function (see Section 8.5.6).

8.5.8 MISSING VALUES

Missing data will not be imputed.

For the ITT analyses of efficacy in the Phase 3 segment, subjects with missing or unevaluable data regarding case definition will be considered cases (failures).

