8.4 ANALYTICAL POPULATIONS

Analysis populations will be:

The per-protocol (PP) population includes all subjects who receive all doses of Study Treatments and have no protocol violations. Subjects in the PP population will be grouped to treatment arms as randomized. Subjects excluded from the PP population will be identified and documented prior to unblinding of the trial database. Analyses on the PP population among those who are baseline SARS-CoV-2 seronegative will be primary for the analyses of efficacy in the Phase 3 segment of this trial.

The modified intention to treat (mITT) population includes all subjects who receive at least one dose of Study Treatment. Subjects in this population will be grouped to treatment arms as randomized. Analysis of the mITT population will be considered supportive for the corresponding PP population for the analyses of efficacy in the Phase 3 segment of this trial.

The intention to treat (ITT) population includes all subjects who are randomized. Subjects in this sample will be grouped to treatment arms as randomized. Analysis of the ITT population will be considered supportive for the corresponding PP population for the analyses of efficacy in the Phase 3 segment of this trial.

The safety analysis population includes all subjects who receive at least one dose of Study Treatment. Subjects will be analyzed according to the treatments received.

8.5 **DESCRIPTION OF STATISTICAL METHODS**

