8.5.1 PRIMARY ANALYSIS

Phase 2 Segment

Post-baseline increases from baseline in interferon-γ ELISpot response magnitudes will be compared between treatment groups using differences in medians and associated non-parametric 95% CIs.

INO-4800	COVID19-311
Inovio Pharmaceuticals, Ind	. Clinical Protocol

Post-baseline increases from baseline in neutralizing antibody response titers will be compared between treatment groups using ratios of geometric mean fold-rises and associated t-distribution based 95% CIs.

The summaries listed above will be stratified according to NP positive/negative status of the subjects. Valid samples for statistical analysis purposes will be those collected: at least 6 and no more than 30 days after Dose 2 for the Week 6 timepoint; at least 174 and no more than 198 days after Dose 2 for the Week 30 timepoint; and at least 356 and no more than 380 days after Dose 2 for the Week 56 timepoint. Baseline is defined as the last measurement prior to the first treatment administration.

The PP population will be used for these immunogenicity analyses.

Phase 3 Segment

Among subjects who are SARS-CoV-2 seronegative at baseline, the primary hypothesis of relative efficacy greater than 30% will be tested with H₀: $p \ge 0.70/(0.70+k)$ vs. H₁: p < 0.70/(0.70+k), where p is the true proportion of subjects with disease who receive INO-4800 relative to the total number of subjects with disease, and k is the total amount of follow-up time in the placebo group divided by the total amount of follow-up time in the INO-4800 group.

A p-value for this hypothesis test and corresponding confidence interval will be computed based on the exact binomial method of Clopper-Pearson. Success will be concluded if the one-sided p-value is <0.022 and the corresponding lower bound of the two-sided 95.6% Cl for efficacy exceeds 30% (alpha-level adjusted for interim analyses, see Section 8.5.6), and the point estimate for efficacy exceeds 50%.

For calculating k, an individual subject's follow-up time is either:

- $\circ~$ the date of first disease diagnosis date of the start of surveillance period +1 (for subjects who are cases), or
- the date of last follow-up date of the start of surveillance period +1 (for subjects who are non-cases).

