This methodology is based on the following. Assuming that the number of subjects who are cases in the INO-4800 group follows a Poisson distribution with parameter λ_v and the number of subjects who are cases in the placebo group follows a Poisson distribution with parameter λ_c , then conditional on total number of subjects with cases, t, the number of subjects who are cases in the INO-4800 group follows a binomial distribution with parameters (t, $p = \lambda_v/(\lambda_v + \lambda_c)$). The relationship between p and efficacy is: efficacy = (1-(1+k)p)/(1-p). Therefore, testing efficacy > 30% corresponds to testing p < 0.70/(0.70+k). Similarly, the confidence interval for efficacy is (1-(1+k)UB_p)/(1-UB_p), (1-(1+k)LB_p)/(1-LB_p), where UB and LB are the Clopper-Pearson upper and lower limits for the proportion.

The efficacy time frame is defined by symptoms beginning at any time starting from 14 days after Dose 2 and ending 12 months after Dose 2. Subjects identified as cases that started prior to this time point will be excluded. Subjects with multiple instances meeting the case definition will be counted only once, using the first such instance.

The PP population will be primary for the analysis of efficacy in this trial. Efficacy analysis using the mITT population will also be conducted counting cases from 14 days postdose 1 as a supportive analysis. The ITT population will also be used for a supportive analysis counting cases starting from randomization.

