8.5.9.3 Concomitant Medications

Concomitant medications are those used during the course of the trial (on or after Day 0). Partial stop dates of concomitant medications will be assumed to be the latest possible date consistent with the partial date; start dates will not be imputed. Data for all concomitant medications will be summarized with percentages by treatment arm, for the ITT and PP populations. These summaries will be performed according to Phase. For the Phase 3 segment, the analyses listed above will also be performed according to SARS-CoV-2 serostatus at baseline.

8.6 **SAMPLE SIZE/POWER**

Phase 3 segment: The trial is case-driven. A total of 149 observed cases among baseline SARS-CoV-2 seronegative subjects will be required to provide 90% power to declare the vaccine efficacious (>30%), assuming a true efficacy of 60% and utilizing the methodology described in Section 8.5.1 and Section 8.5.6. A sample size of 6714 baseline SARS-CoV-2 seronegative subjects will be required to achieve this number of cases assuming an underlying attack rate of 3.7%.

INO-4800	COVID19-311
Inovio Pharmaceuticals, Inc.	Clinical Protocol

8.7 **RANDOMIZATION AND BLINDING**

Phase 2 Segment

Subjects will be randomized (3 INO-4800 1.0 mg, one injection: 3 INO-4800 2.0 mg, two injections:1 Placebo, one injection: 1 Placebo, two injections).

The study is blinded. It is double-blinded within dose group. Randomization and blinding will avoid bias in the assignment of subjects to treatment, increase the likelihood that known and unknown subject attributes (e.g., demographics and other baseline characteristics) are evenly balanced between treatment groups, and enable valid statistical comparisons between treatment groups.

Phase 3 Segment

Subjects will be randomized (2 INO-4800:1 Placebo). Randomization will be stratified according to two factors, each with two levels: a) age-group age category (18-50 years vs. ≥51 years) on Day 0, and b) presence or absence on Day 0 of underlying medical conditions that increase risk of severe COVID-19 disease, per US CDC criteria.

The study is double-blinded. Randomization and blinding will avoid bias in the assignment of subjects to treatment, increase the likelihood that known and unknown subject attributes (e.g., demographics and other baseline characteristics) are evenly balanced between treatment groups, and enable valid statistical comparisons between treatment groups.

9.0 **ETHICS**

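### Counting missing case status as COVID-19 in the supportive Phase 3 ITT analysis makes its efficacy estimate track dropout more than vaccine effect once missingness passes about 2.3%

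*Protocol*

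**What the plan says.** All references are to Protocol Version 5.0.

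- Section 8.5.8 opens with "Missing data will not be imputed". It then provides that, for the Phase 3 ITT efficacy analyses, "subjects with missing or unevaluable data regarding case definition will be considered cases (failures". The rule applies to both arms and is not restricted to subjects who had a suspected episode.
- Section 8.4: "The intention to treat (ITT) population includes all subjects who are randomized". The ITT analysis is supportive to the PP analysis.
- Section 8.5.1: "The ITT population will also be used for a supportive analysis counting cases starting from randomization".
- Section 8.5.1 also defines the follow-up time that enters k, the placebo-to-vaccine ratio of total follow-up. The minus sign between the two dates is lost in the available text. For cases it is "the date of first disease diagnosis date of the start of surveillance period +1". For the rest it is "the date of last follow-up date of the start of surveillance period +1 (for subjects who are non-cases".
- Section 8.6: "A total of 149 observed cases among baseline SARS-CoV-2 seronegative subjects will be required to provide 90% power". It assumes a true efficacy of 60% and an attack rate of 3.7%, and arrives at 6714 seronegative subjects.
- Section 3.0 plans 56 weeks of follow-up from Day 0. Section 4.3 provides for loss to follow-up and states that subjects are not followed after withdrawing consent. No dropout rate is given.

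**The concern.** Setting missing to failure can be tolerable for a common binary response, where failures are numerous anyway. Here true cases are expected in about 2% of subjects, so a few percent with missing case status produce more imputed cases than real ones. With 2:1 allocation and similar missingness by arm, the imputed cases fall about 2:1 as well and carry almost no vaccine effect. If missingness differs between arms, the imputed cases carry that difference instead.

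The method does not need the rule. It compares cases per unit of follow-up, and a non-case already contributes time up to the last follow-up date.

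What is at stake is the value of the ITT analysis. The PP set requires all doses and no protocol violations, so it is open to selection after randomization. The ITT analysis is the only one that keeps everyone randomized. If its estimate is driven mainly by dropout, neither agreement nor disagreement with PP says much about the vaccine.

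**Working it through.** **Inputs from the protocol.** 149 cases; VE 60%; attack rate 3.7%; 6714 seronegative subjects, 4476 vaccine and 2238 placebo; 2:1 allocation, so k is about 0.5.

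**Assumption.** A share d of the subjects who are not true cases has missing case status. Since no rate is stated, d is varied from 1% to 20%.

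**Step 1: reproduce the plan's sample size.** Reading 3.7% as the placebo-arm rate:

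N = 149 / [0.037 × (2/3 × 0.40 + 1/3)] = 149 / 0.0222 = 6711.7, or 6714 as a multiple of 3.

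The figure is reproduced with no allowance for dropout.

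**Step 2: expected true cases.** Vaccine: 4476 × 0.037 × 0.40 = 66.2. Placebo: 2238 × 0.037 = 82.8. Total 149, and 149/6714 = 2.2%.

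**Step 3: where imputed cases equal true cases.** d × (6714 − 149) = 149, so d = 149/6565 = 2.3%.

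**Step 4: VE under the rule, equal missingness.**

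VE = 1 − [0.0148 + d(1 − 0.0148)] / [0.037 + d(1 − 0.037)]

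At d = 5%: 1 − 0.06406/0.08515 = 24.8%. The confidence limits are Clopper-Pearson, transformed with the section 8.5.1 formula at k = 0.5.

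| Missing, both arms | Imputed cases | Share of all counted cases | ITT VE (95% CI) |
|---|---|---|---|
| 0% | 0 | 0% | 60% (44 to 72) |
| 1% | 66 | 31% | 47% (31 to 60) |
| 2% | 131 | 47% | 39% (22 to 52) |
| 5% | 328 | 69% | 25% (9 to 37) |
| 10% | 656 | 81% | 15% (2 to 27) |
| 20% | 1313 | 90% | 8% (−3 to 17) |

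An imputed case has no diagnosis date, so its follow-up time is not defined. Placing all events at mid follow-up changes VE by at most about 1 point, so the dilution does not hinge on that gap.

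**Step 5: unequal missingness.** The formula is the same, with a separate d for each arm.

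| Vaccine missing | Placebo missing | ITT VE |
|---|---|---|
| 10% | 8% | 1 − 0.11332/0.11404 = about 1% |
| 8% | 10% | 1 − 0.09362/0.13330 = about 30% |
| 5% | 10% | 1 − 0.06406/0.13330 = about 52% |

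**Step 6: the alternative.** If dropouts are censored at last follow-up and dropout is non-informative, expected VE stays at 60%. With dropout spread evenly over follow-up, the expected case count falls to about 145, 142 and 134 at 5%, 10% and 20% dropout.

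**The case against.** **No decision rests on this analysis.** This stands. The PP analysis in seronegatives is primary, there is no other formal hypothesis, and power, type I error and interim boundaries are unchanged. A reader might infer that the rule threatens the trial's conclusion, or hold the ITT estimate to the 50% point-estimate criterion. The protocol attaches that criterion to the primary test only.

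**The mITT analysis is a second supportive analysis without the rule.** This also stands, because section 8.5.8 names only the ITT analyses. But mITT requires at least one dose and counts from 14 days after dose 1, so it does not replace the all-randomized analysis.

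**The rule may mean only episodes that could not be adjudicated.** The case definition in section 3.7.1 is a positive RT-PCR plus a symptom, and section 7.11 tracks suspected cases to a determination by the Endpoint Adjudication Committee (EAC). Someone who leaves without an event could then be a censored non-case. The reading is possible, and the scenarios above would not apply under it. Section 8.5.8 does not say so, however, and its wording also fits a subject lost to follow-up.

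**The two sentences of section 8.5.8 need not conflict.** A reader might call them a flat contradiction. A general rule followed by an exception for one analysis is ordinary drafting, and the point does not depend on it.

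**The pull toward zero is not certain.** Correct. It needs similar missingness in both arms, and Step 5 shows movement either way. Nor does the document support saying that ITT will almost certainly contradict PP. No dropout rate is stated, and at 5% and 10% balanced missingness the intervals still exclude zero.

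**The case counts belong to the primary window.** True. ITT counts from randomization, so earlier cases would be added and the ratio of imputed to true cases is approximate.

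**Conclusion.** The concern holds for the supportive ITT analysis and should be fixed. Applied as worded, the rule lets imputed cases outnumber true ones above about 2.3% missing. A true VE of 60% would appear as about 47%, 39%, 25% and 15% at 1%, 2%, 5% and 10% balanced missingness. A modest imbalance between arms can take it to about 1% or 52%.

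These sizes rest on assumed missingness, the sample-size case counts in seronegatives, and the reading that loss to follow-up counts as missing case data. The defect is confined to the ITT analysis. There it removes the use of the only all-randomized analysis as a check on selection into the PP set.

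**What to change.** In section 8.5.8, replace the ITT rule with censoring. Subjects without a confirmed case would contribute follow-up time to their last evaluable contact under the section 8.5.1 formula, and only EAC-confirmed cases would count.

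If missing-equals-case is to be kept, either of these would do:

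- a sensitivity analysis labelled as worst-case or tipping-point, with missingness outcomes varied by arm; or
- a rule restricted to suspected episodes that cannot be adjudicated for lack of a usable RT-PCR result.

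The change is best made before unblinding, since dropping the rule after a diluted ITT result is known would look post hoc. The cost is a revised sentence and one extra sensitivity table, with no new data. Censoring brings its own assumption of non-informative dropout, which the tipping-point table would probe.

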8.5.9 EXPLORATORY ANALYSES

8.5.9.1 Efficacy

Phase 3 segment

The exploratory efficacy endpoints will be analyzed in the same manner as the primary hypothesis, but with a 95% CI and without the hypothesis test p-value.

8.5.9.2 Immunogenicity

Phase 2 segment

INO-4800	COVID19-311
Inovio Pharmaceuticals, Inc.	Clinical Protocol

Post-baseline increases from baseline in cellular response magnitudes will be compared between treatment groups using differences in medians and associated non-parametric 95% CIs.

The summaries listed above will be stratified according to NP positive/negative status of the subjects.

Valid samples for statistical analysis purposes will be those collected: at least 6 and no more than 30 days after Dose 2 for the Week 6 timepoint; at least 174 and no more than 198 days after Dose 2 for the Week 30 timepoint; and at least 356 and no more than 380 days after Dose 2 for the Week 56 timepoint. Baseline is defined as the last measurement prior to the first treatment administration.

The PP population will be used for immunogenicity analyses.

Phase 3 Segment

Post-baseline increases in antibody titers from ELISA will be compared between treatment groups using ratios of geometric mean fold-rises and associated 95% t-distribution based CIs.

Post-baseline increases from baseline in cellular response magnitudes will be compared between treatment groups using differences in medians and associated non-parametric 95% CIs.

Post-baseline increases from baseline in neutralizing antibody response titers will be compared between treatment groups using ratios of geometric mean fold-rises and associated t-distribution based 95% CIs.

The summaries listed above will be stratified according to disease status of the subjects.

Valid samples for statistical analysis purposes will be those collected: at least 6 and no more than 30 days after Dose 2 for the Week 6 timepoint; at least 174 and no more than 198 days after Dose 2 for the Week 30 timepoint; and at least 356 and no more than 380 days after Dose 2 for the Week 56 timepoint. Baseline is defined as the last measurement prior to the first treatment administration.

The PP population will be used for immunogenicity analyses.

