Phase 3 Segment – Efficacy

In the Phase 3 segment, approximately 6714 seronegative and 402 seropositive subjects 18 years of age and older will be randomized at a 2:1 ratio to receive either active investigational product (INO-4800, 1mg) or placebo (SSC-0001). Approximately half of seronegative subjects and approximately half of seropositive subjects will be 18-50 years of age, and the other half will be \geq 51 years of age. Also, a minimum of 10% of the total sample size will be \geq 65 years of age.

Subjects will be randomized in a stratified manner according to (a) age category (18-50 years vs. ≥51 years) on Day 0, and (b) presence of or absence on Day 0 of any of the following underlying medical conditions that increase risk of severe COVID-19 disease, per CDC criteria [1], as listed below:

- Cancer
- Chronic kidney disease
- Chronic lung diseases, including Chronic obstructive pulmonary disease (COPD), asthma (moderate-to-severe), interstitial lung disease, cystic fibrosis, pulmonary hypertension
- Neurologic conditions including stroke or cerebrovascular disease, that do not impact cognition
- Diabetes (type 1 or type 2)
- Hypertension
- Heart conditions, such as heart failure, coronary artery disease, or cardiomyopathies
- HIV infection (CD4 count >200 cells/mm3 or undetectable viral load)
- Liver disease
- Obesity (BMI \geq 30 kg/m2)
- Sickle cell disease or thalassemia, or
- Smoking (current or former smoker).

This segment of the trial is case-driven. Among seronegative subjects, a total of 149 observed cases will be required for 90% power to declare the vaccine efficacious (>30%), assuming a true efficacy of 60%. A sample size of 6714 seronegative subjects is expected to be required to achieve the 149 cases assuming an underlying attack rate of 3.7%. The

INO-4800	COVID19-311
Inovio Pharmaceuticals, Inc.	Clinical Protocol

actual sample size may differ if the observed attack rate is different than projected. There are two formal interim analyses of efficacy; one when 50% of the cases accrue and one when 75% of the cases accrue. If the prespecified criteria for efficacy are met at either interim analysis, then enrollment will continue until 4500 subjects have been enrolled, and blinded follow-up will continue until at least those 4500 subjects have a minimum of 6 months of safety follow-up. At that point, the trial would be unblinded and placeborecipients will be offered the active product.

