3.6 EXPLORATORY ENDPOINTS

Table 8: Exploratory Objectives and Associated Endpoints

Phase 2 Exploratory Objective	Objective Phase 2 Exploratory Endpoints	
1. Evaluate the expanded	1a. Antigen-specific cellular immune response	
immunological profile of antibody	measured by flow cytometry.	

INO-4800	
Inovio Pharmaceuticals, Inc	;.

		7	
	response and T cell immune response	1b. Expanded immunological profile which may include additional assessments of T and B cell numbers and molecular changes by measuring immunologic proteins and mRNA levels of genes of interest as determined by sample availability	
Pł	nase 3 Exploratory Objective	Phase 3 Exploratory Endpoints	
1.	Evaluate the efficacy of INO-4800 in the prevention of COVID-19 disease from SARS-CoV-2 variants in subjects who are SARS-CoV-2 seronegative at baseline	 Incidence of virologically-confirmed COVID-19 disease from a SARS-CoV-2 variant starting 14 days after completion of the 2-dose regimen until 12 months post-dose 2 (End of Study (EOS)) in subjects who are SARS-CoV-2 seronegative at baseline 	
2.	Evaluate the efficacy of INO-4800 in the prevention of SARS-CoV-2 asymptomatic infection in subjects who are SARS-CoV-2 seronegative at baseline	2. Incidence of SARS-CoV-2 asymptomatic infections in SARS-CoV-2 seronegative subjects starting 14 days after completion of the 2-dose regimen until EOS	
3.	Evaluate the immunological profile by assessing both antibody	3a. SARS-CoV-2 Spike glycoprotein antigen- specific binding antibody levels	
	response and T cell immune response	 Antigen-specific cellular immune response measured by flow cytometry 	
4.	Evaluate antibody persistence	4a. SARS-CoV-2 Spike glycoprotein antigen specific binding antibody levels at Week 30 or later.	
		4b. Neutralizing antibody response measured by a pseudovirus-based neutralization assay at Week 30 or later	

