8.5.2.2 Immunogenicity

Phase 3 Segment

Post-baseline increases from baseline in interferon- γ ELISpot response magnitudes will be compared between treatment groups using differences in medians and associated non-parametric 95% CIs.

Post-baseline increases from baseline in neutralizing antibody response titers will be compared between treatment groups using ratios of geometric mean fold-rises and associated t-distribution based 95% CIs.

The summaries listed above will be stratified according to disease status of the subjects and by baseline SARS-CoV-2 serostatus.

Valid samples for statistical analysis purposes will be those collected: at least 6 and no more than 30 days after Dose 2 for the Week 6 timepoint; at least 174 and no more than 198 days after Dose 2 for the Week 30 timepoint; and at least 356 and no more than 380 days after Dose 2 for the Week 56 timepoint... Baseline is defined as the last measurement prior to the first treatment administration.

The PP population will be used for these immunogenicity analyses.

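### The Phase 3 stratification sentence in section 8.5.9.2 was not extended to baseline serostatus when version 5.0 added 402 seropositive subjects, so binding-antibody and flow-cytometry summaries pool the two groups

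*Protocol*

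**What the plan says.** In protocol version 5.0, section 8.5.9.2 (Phase 3) covers three outputs: ELISA antibody titers and neutralizing titers, each compared by ratios of geometric mean fold-rises, and cellular response magnitudes, compared by differences in medians. It then states: "The summaries listed above will be stratified according to disease status of the subjects". On the analysis set it adds: "The PP population will be used for immunogenicity analyses".

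Section 8.5.2.2 (Phase 3) covers ELISpot and neutralizing titers and states: "The summaries listed above will be stratified according to disease status of the subjects and by baseline SARS-CoV-2 serostatus".

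Section 8.4 defines the per-protocol set as one that "includes all subjects who receive all doses of Study Treatments and have no protocol violations". It limits that set to seronegative subjects only for the efficacy analyses. Section 3.0 sets enrolment: "approximately 6714 seronegative and 402 seropositive subjects 18 years of age and older will be randomized at a 2:1 ratio".

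Table 8 (section 3.6) lists binding antibody and flow cytometry under exploratory objective 3. Objective 4, "Evaluate antibody persistence", has endpoint 4a (binding antibody) and endpoint 4b (neutralizing antibody), both at Week 30 or later.

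Sections 8.5.3.1 (adverse events), 8.5.3.2 (vital signs), 8.5.4 (disposition), 8.5.5.1 (demographics) and 8.5.5.2 (prior medications) all add a Phase 3 split by baseline serostatus. So does section 8.5.9.3, which immediately follows the section at issue: "For the Phase 3 segment, the analyses listed above will also be performed according to SARS-CoV-2 serostatus at baseline".

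**The concern.** A fold-rise is measured from the subject's own baseline. A subject who enters already antibody-positive starts from a level raised by past infection, so the same fold-rise means something different than in a naive subject. If the two groups respond differently, the pooled ratio depends on how many seropositive subjects happen to be among those assayed. At Weeks 30 and 56, waning of natural antibody in seropositive placebo subjects can also move the comparator.

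The omission looks like an amendment oversight. The 8.5.9.2 sentence is unchanged from version 4.0, where a positive serologic test at Screening was an exclusion and no serostatus split was needed. Version 5.0 added the seropositive cohort and put the split into the other Phase 3 descriptive summaries, but not into this one, where prior infection bears directly on the measured quantity.

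**Working it through.** **Step 1. Can the text be read as already covering serostatus?** No. Section 8.5.2.2 names disease status and baseline serostatus as two separate factors, so the first does not include the second. The per-protocol definition in 8.4 does not remove seropositive subjects either.

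**Step 2. Which outputs have no stratified version?**

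| Output | Rule in 8.5.2.2 | Rule in 8.5.9.2 | Stratified by serostatus somewhere? |
|---|---|---|---|
| ELISA binding antibody (3a, 4a) | not covered | disease status only | No |
| Flow cytometry (3b) | not covered | disease status only | No |
| Neutralizing titers, including Week 30 or later (4b) | disease status and serostatus, with Week 30 and 56 windows | disease status only | Yes, through 8.5.2.2 |

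**Step 3. The seropositive share.** From Table 2: 4476 + 2238 = 6714 seronegative; 268 + 134 = 402 seropositive; 6714 + 402 = 7116, as the protocol states. The planned share is s = 402/7116 = 5.65%. It is the same in each arm: 268/4744 and 134/2372.

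**Step 4. Effect on a fold-rise ratio.** The protocol gives no fold-rises by serostatus, so these are assumptions. Within an arm, the pooled geometric mean is F_neg^(1−s) × F_pos^s, and the reported ratio is vaccine over placebo.

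- Seropositives respond less (vaccine 10 in seronegatives and 2 in seropositives, placebo 1 in both): 10^0.9435 × 2^0.0565 = 9.13, against 10 in seronegatives (−9%).
- Seropositives respond more (vaccine 5 in seronegatives and 20 in seropositives; placebo 1 and, with waning, 0.7): vaccine 5 × 4^0.0565 = 5.41; placebo 0.7^0.0565 = 0.980; ratio 5.5, against 5.0 in seronegatives (+10%).
- Milder contrasts: ratios of 5 and 2 pool to 4.75 (−5%); ratios of 3 and 10 pool to 3.21 (+7%).
- Equal ratios in the two groups: no shift.

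This arithmetic applies to antibody titers only. Flow-cytometry changes are compared by medians, so pooling mixes the groups there too, but no size can be put on it from these formulas.

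**Step 5. The subjects actually assayed.** Section 6.5 has humoral and cellular analysis done in the first 102 subjects aged 18-50 and the first 102 aged 51 or older at selected sites (204 in all), plus subjects with COVID-19 when samples are available. It sets no serostatus rule. A proportional share would be 204 × 402/7116 = 11.5 subjects. Under exclusion criterion b of section 4.2.2, seropositive subjects are accepted until about 402 are randomized, so the earliest enrollees could include more than 5.65%. Serostatus is not a randomization stratum in section 8.7.

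**The case against.** Much of the opposing case stands. The outputs are exploratory and descriptive; section 8.3 has no formal hypothesis beyond the primary. The serostatus data are collected, so the split could be produced at any time. At the planned share the shift is also small beside sampling error. With 204 subjects at 2:1 (136 and 68) and an assumed log10 SD of 0.5, the standard error of the log10 ratio is 0.5 × √(1/136 + 1/68) = 0.074, a 95% interval of about a factor of 1.4 either way. The shift from 10 to 9.13 is 0.039 on that scale, about half a standard error. The pooled ratio is still a randomized comparison of the enrolled mixture.

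Deferring the matter to a separate SAP does not work here. Section 8.1 says the formal plan is contained in these sections, and 8.5.9.2 states a specific rule that differs from its counterpart.

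Four stronger readings are tempting but not supported:

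- **Antibody persistence as a whole lacks the split.** Endpoint 4b is covered by 8.5.2.2. Two tables of the same neutralizing data under different rules are untidy, but the stratum results exist.
- **The distortion is large.** At an assumed 30% share, ratios of 5 and 2 would pool to 3.80 (−24%) and ratios of 3 and 10 to 4.31 (+44%). No section gives a share near 30% for the assayed subset.
- **Table 8 is itself at fault because objectives 3 and 4 are not limited to seronegatives.** Secondary objective 3 in Table 7 is equally unrestricted; there the split is made in the analysis section.
- **The seronegative stratum must be named the main result.** Section 8.5.2.2 does not do so even for the secondary endpoints.

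**Conclusion.** The inconsistency is real in the current text and minor in consequence. Followed as written, section 8.5.9.2 yields binding-antibody results (including endpoint 4a) and flow-cytometry results that mix seropositive and seronegative subjects, with no stratified counterpart. Neutralizing titers are reported under two rules, one of them stratified.

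At the planned 5.6% share, the fold-rise ratio shifts by roughly 5% to 10% in either direction under the assumed responses, and not at all if the two groups respond alike. These sizes rest on assumed fold-rises and on the assayed subset matching the overall share. A larger effect is possible because the subset has no serostatus rule, but the protocol gives nothing from which to size it. The primary efficacy analysis, its alpha and its power are not touched.

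**What to change.** In the Phase 3 part of section 8.5.9.2, append "and by baseline SARS-CoV-2 serostatus" to the stratification sentence, so that it matches 8.5.2.2. This also puts the two neutralizing-titer summaries under one rule. The cost is one phrase and one further table split on data already collected, with no change to sample size or testing. At a proportional share the seropositive stratum of the 204 would hold only about 8 vaccine and 4 placebo subjects (11.5 × 2/3 and 11.5 × 1/3). The practical gain is therefore a clean seronegative estimate rather than a precise seropositive one.
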